7.4. Vital Signs

Vital signs (including body temperature and blood pressure) will be collected throughout the study.

Vital signs results will be classified into 4 or 5 categories (low, borderline low, normal, borderline high, or high) according to [Table 4](#) below. Shift tables based on this classification will be summarized from baseline to the last post-baseline visit value.

Table 4: Classification of Vital Signs

Vital Sign	Low	Borderline Low	Normal	Borderline High	High
Systolic BP (mmHg)	< 80	-	80-120	121-139	≥ 140
Diastolic BP (mmHg)	< 60	-	60-80	81-89	≥ 90
Temperature (°C)	< 35.0	35.0-36.4	36.5-37.2	37.3-37.9	≥ 38.0

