- ^f ECOG, PE, pregnancy test for WCBP, and hematology and chemistry labs (if all parameters are within normal range) do not need to be repeated at C1D1 if performed within the previous 4 days during Screening.
- ^g Vital signs (BP and body temperature) will be measured before start of infusion; post infusion vital signs should be collected as clinically indicated for potential infusion-related reaction.
- ^h Hematology and chemistry labs may be performed up to 4 days prior to D1 of each cycle, and as clinically indicated while on treatment, with results reviewed before each MIRV administration. In the event of severe toxicity, laboratory tests must be repeated as clinically necessary until the toxicity resolves or stabilizes to baseline level.
- ⁱ Performed between 3 and 6 months after EOT based on patient availability or until documented progression (as measured by CA-125 GCIG criteria and/or RECIST-defined measurable disease).
- ^j For WCBP, a urine or serum pregnancy test must be performed within the 4 days prior to D1 of each cycle, and at the 30-Day Follow-up visit. It is recommended to perform monthly pregnancy tests for 3 months after the last dose of MIRV. Additional testing may be performed in accordance with institutional requirements or local regulation.
- ^k Baseline ophthalmic exams will be performed by an ophthalmologist within 14 days before C1D1 and will include the following: visual acuity (with/without corrective lens; whichever best reflects the patient's usual functioning), slit lamp examination, and intraocular pressure measurement. All patients who have an ophthalmic exam on study treatment (post-baseline) due to emergence of visual signs or symptoms will have a complete ophthalmological examination performed at EOT visit or 30-Day Follow-up visit.
- ^l Ocular symptoms assessment will be performed by the treating physician or other qualified individual before the start of each cycle. For patients reporting > CTCAE Grade 1 ocular symptoms, treatment will be held until the patient is evaluated by an ophthalmologist for a complete examination.
- ^m Radiologic tumor assessment by CT/MRI scan. The same method of radiographic assessment used at Screening must be used at all subsequent radiographic assessments.

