9.3. Follow-up Assessments

9.3.1. 30-Day Follow-up Visit

A 30-Day Follow-up visit will occur 30 days (+14 days) after last dose of MIRV and should occur prior to the start of new anticancer therapy.

In some cases, nonserious AE observations may continue beyond the safety visit. All ocular AEs will be followed until resolution, stabilization, or return to baseline. In these instances, additional information may be requested by ImmunoGen to adequately categorize the nature of the toxicity.

All SAEs will be followed until they resolve, stabilize, or return to baseline, regardless of time from last dose or last visit.

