4.2. Definition of Baseline

Study Day 1 (ie, Cycle 1 Day 1) will be designated as the first day a patient receives MIRV. The baseline value is defined as the last non-missing value on or before the date of first dose of MIRV.

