4.4. Multiple Assessments for the Same Assessment Time Point

In the case of multiple observations at a specific visit, the first non-missing measurement will be used for analysis, unless multiple study assessments are expected (e.g., pre-dose vs post-dose). When multiple study assessments are expected, the first non-missing measurement for the visit and assessment time point will be used for analysis.

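### The SAP's vital-sign shift table stops at the last post-baseline value, so transient on-treatment highs and lows do not appear in it

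*SAP*

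**What the plan says.** SAP 7.4 sets cut-points for systolic pressure, diastolic pressure and temperature (its Table 4). It then specifies one kind of table, in which category shifts are "summarized from baseline to the last post-baseline visit value". It defines no worst-value shift and no on-treatment window.

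SAP 4.2 fixes the starting point by date: "The baseline value is defined as the last non-missing value on or before the date of first dose of MIRV". SAP 4.4 covers several readings at one visit: "the first non-missing measurement will be used for analysis, unless multiple study assessments are expected (e.g., pre-dose vs post-dose"), in which case "the first non-missing measurement for the visit and assessment time point will be used for analysis".

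Protocol Table 2 marks vital signs at Screening, Day 1 of each cycle, EOT and the 30-Day Follow-up. Its footnote g says "Vital signs (BP and body temperature) will be measured before start of infusion", and adds that "post infusion vital signs should be collected as clinically indicated for potential infusion-related reaction". Protocol 9.3.1 sets the final safety visit: "A 30-Day Follow-up visit will occur 30 days (+14 days) after last dose of MIRV".

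Protocol 10.2 promises more than SAP 7.4 does: a listing of every vital-sign assessment by patient, descriptive statistics for selected criteria, and a summary of changes from baseline. Vital signs are part of an additional secondary (safety) endpoint in Protocol 2.2.3 and SAP 3.1.3.3.

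**The concern.** A safety shift table is normally read to see whether patients moved into an abnormal category while exposed to the drug. A table that ends at the last available value answers a different question, namely where patients ended up. Once a patient has stopped MIRV and come back for EOT or the 30-Day Follow-up, that value was taken after the final dose. A rise in blood pressure, a fall in blood pressure or a fever that came and went during treatment is then counted as no change.

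What is at stake is the usefulness of one descriptive display. No hypothesis test, stopping rule or efficacy estimate depends on it.

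**Working it through.** The plan gives no figure to reproduce. The check sets the passages side by side, with day arithmetic on the visit windows.

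**1. When the last scheduled reading falls.**
- Inputs: follow-up visit at 30 days (+14) after the last dose (Protocol 9.3.1); dosing every 21 days (Protocol 4.1.1); a limit of 30 days after the last dose for treatment-emergent AEs (SAP 7.2) and for Grade 3 or higher laboratory values (SAP 7.3).
- Range after last dose: 30 to 30 + 14 = 44 days.
- Relative to when the next dose would have been due: 30 − 21 = 9 to 44 − 21 = 23 days later.
- Beyond the SAP's 30-day safety limit: 0 to 44 − 30 = 14 days.

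EOT comes within 7 days of the decision to discontinue (Protocol 9.2), so it also follows the final dose.

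**2. What the table does with a transient change.** Take, for illustration, a patient with normal systolic pressure at baseline, 150 mmHg at Day 1 of Cycles 2 to 6, and a normal value at the 30-Day Follow-up. SAP Table 4 classes 140 mmHg or more as high, so five consecutive scheduled readings are high. The shift table records normal to normal.

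**3. What other SAP safety displays do.**

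| Data | Value used |
|---|---|
| Grade 3+ laboratory values (SAP 7.3) | Worst, on treatment or within 30 days of last dose |
| Liver function tests (SAP 7.3) | Maximum on MIRV; also worst post-baseline grade |
| Best corrected visual acuity shift (SAP 7.8) | Worst post-baseline and last exam |
| Vital-sign shift (SAP 7.4) | Last only |

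The closest parallel is visual acuity, where the SAP shows worst and last together. The laboratory comparison is looser: the general laboratory shift sentence does not name a worst value, and a shift table for liver tests is expressly not produced.

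**4. Where a transient change would still be seen.** Protocol 8.1.1.1 makes clinically significant vital-sign abnormalities adverse events, and SAP 7.2 tabulates treatment-emergent events by term and grade. Protocol 10.2 adds the listing and the change-from-baseline summary. SAP 7.4 omits both, and SAP Section 9, which records departures from the protocol, mentions only the timing of the ORR analysis. They are therefore neither carried forward nor withdrawn.

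**5. Baseline.** SAP 4.2 read alone would admit a reading taken after the infusion on Day 1. Against that, the scheduled Day 1 reading is before the infusion, post-infusion readings are taken only on clinical indication, and the first-measurement rule in SAP 4.4 would normally select the pre-infusion value. The exception in 4.4 for expected pre-dose and post-dose assessments leaves a loose end, because 4.2 and 4.4 are not tied together.

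**The case against.** The strongest reply is that this is a preference about one descriptive table. Three points in it stand.

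- A reader might infer that on-treatment changes are hidden, or that the trial cannot show drug-related hypotension, hypertension or fever. The documents do not support that: clinically significant abnormalities are tabulated as adverse events, and Protocol 10.2 still promises listings and change-from-baseline summaries. AE reporting is only a partial substitute, because a reading that SAP Table 4 calls high need not be judged clinically significant.
- A reader might infer that the last value is usually off drug. That depends on data maturity and attendance. Patients still on MIRV at the data cutoff, and those with no visit after stopping, contribute an on-treatment value.
- A reader might infer that baseline is contaminated in patients with infusion reactions. SAP 4.4 and the pre-infusion schedule make this an ambiguity in wording, confined to patients with a post-infusion reading at the first infusion. No distortion is shown.

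The reply also bears on the remedy. Scheduled cycle readings are taken before the infusion, nominally about 21 days after the previous dose. A worst-value table would mix these with post-infusion readings taken only when a reaction is suspected. A cutoff at exactly 30 days would also drop follow-up visits held on days 31 to 44. Both points are right and are built into the fix.

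The reply does not remove the main point: the one vital-sign table that SAP 7.4 specifies omits resolved on-treatment shifts, and the data to show them are already collected.

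**Conclusion.** The concern holds in a limited form. For patients who have stopped MIRV and attended EOT or the 30-Day Follow-up, the SAP 7.4 shift table compares baseline with an off-treatment value, so transient on-treatment highs and lows are absent from that table. The share of patients affected cannot be derived from the documents; it depends on how many have stopped and returned by the cutoff. The conclusion assumes that scheduled visits are attended as Table 2 sets out.

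The gap is in one display, not in the trial's safety capture. The baseline wording needs a clarification and is not an established error. The primary ORR analysis is not affected, and severity is minor.

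**What to change.** 1. **SAP 7.4, shift tables.** Keep the shift to the last value. Add shifts from baseline to the highest and to the lowest post-baseline category, from first dose through the 30-Day Follow-up visit including its +14-day window. Flag unscheduled post-infusion readings, because they are taken only when a reaction is suspected. State that these two tables are an exception to the first-measurement rule in SAP 4.4, which could otherwise discard those readings.
2. **SAP 7.4, other outputs.** Carry over the Protocol 10.2 per-assessment listing and change-from-baseline summary.
3. **SAP 4.2 or 7.4, baseline.** State that the vital-sign baseline is the last non-missing value before the start of the first infusion. This reconciles 4.2 with 4.4.

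No new data are needed. The cost is a few SAP phrases and two more descriptive shift tables, plus the outputs that the protocol already promises. The downside is that highest and lowest values over repeated readings pick up some random variation, so the new tables should be read beside the last-value shift and the AE tables.

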7.5. ECGs

ECG will be performed at screening visit only. All ECG results will be presented in data listings.

7.6. Concomitant Medications

All medications and supportive therapy taken within 4 weeks prior to Cycle 1 Day 1 and through 30 days after last study treatment must be recorded on the appropriate CRF. The identity of all medications, dosage, route of administration, frequency, duration of administration, and indication for use will be recorded in the appropriate sections of the CRF.

Prior medications are defined as medications with a stop date prior to the first dose of MIRV.

Concomitant medications are defined as medications which are taken during the course of study treatment and within 30 days of the last dose of MIRV, as follows:

- Medications started before the first dose of MIRV, but with a stop date after the first dose of MIRV and within 30 days of the last dose of MIRV will be considered concomitant medications.
- Medications started before the first dose of MIRV that are ongoing will be considered concomitant medications.
- Medications started after the first dose of MIRV and within 30 days of the last dose of MIRV or before the start of a new anti-cancer treatment, whichever occurs first, are considered concomitant medications.
- Medications started before the first dose of MIRV, but with a stop date after the first dose of MIRV and within 30 days of the last dose of MIRV or prior to the start of a new anti-cancer treatment, whichever occurs first, will be considered concomitant medications.

Prior and concomitant medications will be coded using the March 2021 or later version of World Health Organization drug dictionary (WHO Drug). Summary tables will be provided for prior and concomitant medications.

Summary tables will be organized to display the anatomical main class of each coded medication (ATC Level 1 term) and, within that, the pharmacological subgroup (ATC Level 3 term) of the coded medication. The summary table will display the number and percentage of patients who reported using at least 1 medication in each represented pharmacological subgroup. If a patient has more than 1 medication in the subgroup, the patient will be counted only once.

A complete listing of medications will be generated by patients. The listing will indicate which medications are prior and which are concomitant. The listing will display entries from the concomitant medications form, ordered within patient by start date. The listing will display the recorded term from the CRF and the WHO Drug anatomical main class (ATC Level 1 term) and pharmacological subgroup (ATC Level 3 term).

7.7. Concomitant Procedures

All procedures within 4 weeks of Cycle 1 Day 1 and through 30 days after last study treatment must be recorded on the appropriate CRF.

Prior procedures are defined as occurring before the first dose of MIRV (by procedure date).

Concomitant procedures are defined as procedures with a procedure date on or after the first dose of MIRV, and within 30 days of the last dose of MIRV or prior to the start of a new anti-cancer treatment, whichever occurs first.

Prior and concomitant procedures will be coded using MedDRA (Version 24.0 or later), associating lower-level terms with PT and SOC by the primary hierarchy. Summary tables will be provided for prior and concomitant procedures. The tables will display the number and percentage of patients who reported at least 1 procedure in each SOC represented in the CRF data. Within each SOC, the tables will display the number and percentage of patients reporting at least 1 concomitant procedure as designated by PT.

A complete listing of procedures will be provided. The listing will indicate which procedures are prior and which are concomitant. The listing will display entries from the concomitant procedures form, ordered within patient by date of procedure. The listing will display the recorded term from the CRF and the SOC and PT.

7.8. Ophthalmic Examinations

A baseline ophthalmic examination will be performed at Screening. Patients who experience ocular TEAEs while on study will have a complete ophthalmologic exam performed at the emergence of the symptoms and at every other cycle thereafter. All patients who have an ophthalmic exam on study treatment (post-baseline) will have a complete ophthalmologic exam performed at the EOT Visit or 30-Day Follow-up Visit. Results of the ophthalmic examinations will be presented in data listings.

Worst decline in both left and right eye best corrected visual acuity (BCVA) grade will be summarized. Shift of both left and right eye BCVA from baseline to worst post baseline and the last ophthalmic exam will be summarized using the following categories: more than two lines of

improvement, two lines improvement, one line of improvement, less than one line change in visual acuity, one line worsening, two lines worsening, more than two lines of worsening.

Intraocular pressure elevations will be summarized by the number of subjects with 7 mmHg elevations or greater post baseline.

7.9. Ocular Symptom Assessments

Results of the ocular assessments will be presented in data listings.

7.10. Corticosteroid and Lubricating Eye Drop Compliance

All compliance information collected on the CRF will be presented in data listings.

7.11. Transfusions

All transfusions recorded on the CRF will be presented in data listings.

7.12. Physical Examination

Physical examination results will be presented in data listings.

7.13. ECOG

ECOG performance status results will be summarized by visits and presented in data listings.

8. IMMUNOGENICITY

Anti-MIRV seroconversion refers to the development of detectable antibodies that bind to MIRV and is based upon positive results in both screening and confirmatory assays. Patients will be classified as follows:

- Treatment emergent ADAs: Patients who had a baseline-negative ADA result who developed ADAs at any time after initial administration of drug.
- Treatment-enhanced ADAs: Patients who had a baseline positive ADA result in whom the assay signal was enhanced (greater than baseline titer by 4 folds) at any time after initial drug administration.
- Treatment-unaffected ADA: Patients who had a baseline-positive ADA result in whom the assay signal was not enhanced (not greater than baseline titer by 4 folds) at any time after initial drug administration.
- Seronegative: a patient who tests negative at baseline and all subsequent visits.

If a titer is below LLQ, it will be imputed as half of LLQ.

The percentage of patients in each category will be summarized using descriptive statistics.

TEAEs by SOC and PT by ADA status will be provided.

Efficacy endpoints ORR and DOR will be analyzed by the above ADA status group.

Neutralizing ADA results will be listed if data are available at the final analysis. All ADA results will be presented in data listings.

The exploratory biomarker analyses for this study will be covered by a separate, independent analysis plan.

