- ⁿ If a patient discontinues before documentation of PD, a tumor assessment and CA-125 will be assessed at the EOT or 30-Day Follow-up visit, if not performed within the previous 6 weeks. Tumor assessments and CA-125 will continue to be performed every 12 (\pm 3) weeks until PD is documented per RECIST v1.1 or the patient starts new anticancer therapy. Patients who discontinue MIRV for reasons other than PD will continue with tumor assessments until documentation of PD or the start of a new anticancer therapy, whichever comes first. Prior to Week 36 (from C1D1), assessments should occur every 6 weeks (\pm 1 week) as allowed by local requirements but must occur at an interval of no more than 12 weeks. After Week 36, assessment will occur every 12 weeks (\pm 3 weeks) until documentation of PD, death, the start of new anticancer therapy, or patient's withdrawal of consent (whichever occurs first).
- ^o CA-125 will be measured at the time of every tumor assessment (\pm 4 days) (responses will be confirmed according to GCIG criteria [Appendix C](#)).
- ^p All SAEs, and those AEs assessed by the Investigator as at least possibly related to study drug should continue to be followed until they resolve or stabilize, whichever comes first.

Document ID: CLIN-00067	Title: IMGN853-0419 Clinical Study Protocol	Version: 2 . 0
Legacy ID: 26587		Approved Date: 12/22/2021

^q Only AEs/SAEs which are considered related to a study procedure (ie, blood draw or fresh tumor biopsy) will be captured during the Pre-screening period, ie, from the time of signing the Pre-screening consent (if one is utilized) until the signing of the main study informed consent, or until the patient is determined to be a screen failure.

^r Immunogenicity will be assessed in samples collected prior to dosing (predose) on C1D1, C2D1, C3D1, C5D1, at EOT, and 30-Day Follow-up.

^s Survival follow-up assessments will occur every 3 months (± 1 month) until death, the patient is lost to follow-up or withdrawal of consent for survival follow-up, or EOS (whichever comes first). These assessments may be conducted by telephone. Information on the start of new anticancer therapy (including start date, therapy type/name, and response on treatment) should be collected. Additional survival follow-up calls may occur periodically if needed for regulatory requests or at time of database lock for either primary or final analysis.

Document ID: CLIN-00067	Title: IMGN853-0419 Clinical Study Protocol	Version: 2.0

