4. INVESTIGATIONAL PLAN

4.1. Study Design

4.1.1. Overview and Schema

This Phase 2 study is designed to evaluate the efficacy and safety of MIRV in patients with recurrent platinum-sensitive, high-grade serous EOC, primary peritoneal, or fallopian tube cancer, whose tumors express a high level of FR α . Patients will have had at least 2 prior lines of therapy. These will include at least 2 lines of platinum-containing therapy or 1 line with a documented platinum allergy. All patients will be, in the opinion of the Investigator, appropriate for non-platinum single-agent therapy for their next line of therapy. FR α positivity will be defined by the Ventana FOLR1 (FOLR1-2.1) CDx assay (Ventana FOLR1 Assay).

The study is designed to test the null hypothesis that the ORR is $\leq 28\%$ using an optimal Simon's two-stage design ([Simon 1989](#)) without a planned pause in enrollment given preliminary efficacy and established safety of MIRV. Approximately 75 patients will be enrolled so that a total of 69 patients will be efficacy evaluable.

Efficacy evaluable patients include those who have at least 1 measurable lesion (per RECIST v1.1) at baseline and received at least 1 dose of MIRV.

All patients will receive single-agent MIRV at 6 mg/kg AIBW ([Appendix D](#)) administered through IV infusion on Day 1 of every 3-week cycle (Q3W).

Computerized tomography (CT) or magnetic resonance imaging (MRI) scans will be collected for sensitivity analysis by BICR.

Patients will continue to receive MIRV until PD, unacceptable toxicity, withdrawal of consent, death, or until the Sponsor terminates the study (whichever comes first).

Tumor assessments, including radiological assessment by CT/MRI scans, will be performed at Screening and subsequently every 6 weeks (± 1 week) from Cycle 1 Day 1 (C1D1) for the first 36 weeks then every 12 weeks (± 3 weeks) until PD, death, the start of new anticancer therapy, or patient's withdrawal of consent, whichever occurs first.

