6. IMMUNOGENICITY AND BIOMARKER ASSESSMENTS

6.1. Immunogenicity Assessments – Mirvetuximab Soravtansine

The potential immunogenicity against MIRV will be assessed at C1D1, C2D1, C3D1, C5D1, EOT, and 30-Day Follow-up, as outlined in [Table 2](#). The potential impact of immunogenicity on the safety and efficacy of MIRV and total Ab will be explored.

An ADA sample should be collected prior to dosing on C1D1. The sample for ADA analysis is taken predose on Day 1 of Cycles 2, 3, and 5 and at the EOT and 30-Day Follow-up visits.

Document ID: CLIN-00067	Title: IMGN853-0419 Clinical Study Protocol	Version: 2.0
Legacy ID: 26587		Approved Date: 12/22/202

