4.12.6. ADA-Evaluable Population

The ADA-Evaluable population includes all patients in the safety population who had baseline and at least one valid post baseline ADA result.

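### Analysing ORR and DOR by ADA status reached at any time can create a false association with efficacy, or hide a true one, if ADA onset is late and most responders are off treatment

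*SAP*

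**What the plan says.** SAP 8 sorts patients into four ADA classes. Treatment-emergent ADA means: "Patients who had a baseline-negative ADA result who developed ADAs at any time after initial administration of drug". The main comparator is "Seronegative: a patient who tests negative at baseline and all subsequent visits". The section then plans that "Efficacy endpoints ORR and DOR will be analyzed by the above ADA status group". The analysis set needs little follow-up (SAP 4.12.6): "The ADA-Evaluable population includes all patients in the safety population who had baseline and at least one valid post baseline ADA result".

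Sampling is set in Protocol Table 2, footnote r: "Immunogenicity will be assessed in samples collected prior to dosing (predose) on C1D1, C2D1, C3D1, C5D1, at EOT, and 30-Day Follow-up". Protocol 6.1 agrees. With 3-week cycles the on-treatment samples fall at weeks 0, 3, 6 and 12. After that nothing is drawn until the patient stops. Protocol 4.1.1 links response to time on drug: "Patients will continue to receive MIRV until PD, unacceptable toxicity, withdrawal of consent, death, or until the Sponsor terminates the study".

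The association of ADA with safety and efficacy is an exploratory endpoint (Protocol 2.2.4, SAP 3.1.3.4). Neither document gives a landmark, a time-dependent ADA status or an exposure adjustment for it.

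**The concern.** Both main groups are defined by what happens after treatment starts. To be classed as treatment-emergent a patient must stay under observation long enough to turn positive. To be seronegative she must stay negative for as long as she is observed. Response prolongs treatment, so the grouping depends partly on the outcome that it is used to describe. A patient whose ADA first appears months after her response still counts as an ADA-positive responder. For DOR the loop is tighter, because a longer response is itself more time in which to become positive. This is guarantee-time (immortal-time) bias.

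At stake is the reading of one exploratory table. A favourable artefact could offset a real loss of efficacy in ADA-positive patients and be taken as reassurance. SAP version 2.0 was issued to add the ADA-evaluable population (SAP 10), so the analysis is evidently meant to be reported.

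**Working it through.** **Figures in the documents.** They state none for ADA by efficacy. The ORR of 48% used below is the design alternative in Protocol 10.1. That design (28 patients with futility at 9 or fewer, then 69 with more than 26 needed) reproduces exactly: early termination 0.762, expected size 37.74, alpha 0.0245, power 0.900. It plays no further part here.

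**Simulation.** 1,000,000 patients per scenario, ADA onset independent of response (no true effect), with the protocol's own sampling schedule. These inputs are assumptions:
- non-responders progress at weeks 6, 12, 18 and 24 in proportions 45%, 30%, 15% and 10%;
- response occurs at week 6;
- DOR is exponential with median 8 months, varied from 4.1 to 15.7, the Phase 1 medians for partial and complete responders in Protocol 1.5.1;
- 5% of patients are ADA-positive by week 12, varied to 2% and 10%.

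**Conversion to apparent ORR.** Let a and b be the proportions ever ADA-positive among responders and non-responders.
- ORR in ADA-positive = 0.48a / (0.48a + 0.52b)
- ORR in ADA-negative = 0.48(1−a) / [0.48(1−a) + 0.52(1−b)]

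Scenario A: 0.48 × 0.208 = 0.0998 and 0.52 × 0.052 = 0.0270, so 0.0998 / 0.1269 = 79%. For ADA-negative, 0.380 / (0.380 + 0.493) = 44%.

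Scenario D: 0.0240 / (0.0240 + 0.0208) = 54%. For ADA-negative, 0.456 / (0.456 + 0.499) = 48%.

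| Scenario, no true ADA effect | a | b | ORR, ADA+ vs ADA− | Median DOR, ADA+ vs ADA− (months) |
|---|---|---|---|---|
| A. Constant hazard, all off treatment | 20.8% | 5.2% | 79% vs 44% | 15.8 vs 6.6 |
| B. As A, half of responders still on drug | 12.8% | 5.2% | 69% vs 46% | – |
| C. As A, all responders still on drug | 4.7% | 5.3% | 46% vs 48% | – |
| D. Onset only in weeks 1–12, all off treatment | 5.0% | 4.0% | 54% vs 48% | 8.0 vs 8.0 |
| E. Onset only in weeks 1–6, all off treatment | 5.0% | 5.0% | 48% vs 48% | 8.0 vs 8.0 |

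Table values come from unrounded simulation output. DOR is shown only where all treatment is complete.

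**Sensitivity of A.** Median DOR 4.1 months gives 70% vs 46%, and 15.7 months gives 85% vs 40%. With 10% ADA-positive by week 12 it is 76% vs 40%.

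**Why the sign can change.** Responders average 4.9 post-baseline samples against 3.8 for non-responders once everyone is off treatment. If all responders are still on drug it is 2.9 against 3.8, because their late samples do not yet exist.

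**How likely is C?** SAP 4.9 waits for six assessments in patients without an earlier terminal event, about 6 × 6 = 36 weeks. That is 30 weeks after a week-6 response, or 6.9 months. The fraction still in response is 0.5^(6.9/median): 31%, 55% and 74% for medians of 4.1, 8 and 15.7 months. This is for the last patient enrolled, and earlier patients are further along. Protocol 10.3.2 updates DOR 12 months later.

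**Effect of a landmark.** Classifying ADA at C3D1 in scenario A gives ORR 48% vs 48% and median DOR 7.9 vs 8.0 months. Across all scenarios the ORR groups stay within about 1 point. C5D1 should behave alike for the same reason: everyone compared has had equal exposure and sampling. The C5D1 version was not simulated.

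**Numbers available.** Expected ADA-positive among 69 = 69 × (1 − exp(−rate × months)), with C3D1 at 1.38 and C5D1 at 2.76 months. At assumed rates of 0.5% to 1% per month this gives 0.5 to 0.9 at C3D1 and 0.9 to 1.9 at C5D1. At 5% by week 12 it gives 69 × (1 − √0.95) = 1.7 at C3D1 and 69 × 0.05 = 3.5 at C5D1. All are upper limits, since they ignore patients who stop before the landmark.

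**The case against.** A reader might infer that the planned table must show a spurious benefit of ADA. The documents do not support that. On-treatment sampling ends at week 12, so a responder's extra exposure counts only once she has stopped and given the late samples. If antibodies form early there is little or no artefact, and if all responders are still on drug the ORR difference slightly reverses. The large figures need an onset hazard that persists for months, and nothing in the documents establishes one. The Protocol's Summary of Changes calls ADA uncommon and gives no rate. This objection stands, and it limits the point to what can happen.

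It is also fair that the consequences are small. The analysis is exploratory, and SAP 8 sets no test or decision rule between ADA groups. The ADA-positive group may be so small that two responders in four would carry an exact 95% interval of 7% to 93%. All ADA results will be listed, so timing can be read patient by patient. That stands as to importance. It does not answer the bias, since small numbers make an estimate imprecise without removing its tilt.

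The remedy has limits too. A C3D1 landmark alone may leave an empty ADA-positive group. The first scan, at week 6 ± 1, can precede the C3D1 sample, so a landmark equalises exposure but does not prove that ADA came before response.

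**Conclusion.** The concern holds as a possibility that the plan leaves open. Grouping ORR and DOR by any-time ADA status lets the length of treatment influence the grouping, and nothing in either document corrects for it. With no true effect, the apparent ORR difference between ADA-positive and ADA-negative patients runs from +35 points (79% vs 44%) through +6 and 0 to about −2 (46% vs 48%). DOR is distorted where the hazard persists (15.8 vs 6.6 months) and is undistorted where onset is confined to the first 6 or 12 weeks and all treatment is complete. Which case applies depends on ADA rate, onset timing and the share of responders still on drug, all assumed here.

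The stronger readings, that a false association will appear or that ADA will necessarily look harmless, go beyond the documents. The primary ORR test is untouched, and so is the overall DOR analysis, because neither uses ADA status. This is a minor but easily corrected weakness in an exploratory analysis.

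**What to change.** Amend SAP 8 as follows.

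- Keep the any-time classes for reporting ADA incidence.
- For ORR, classify ADA from samples up to and including C5D1, among patients still on treatment then. Repeat at C3D1 as a check.
- For DOR, use the same landmark and count duration from it among patients still in response, or treat ADA as a time-dependent status. State how responses first seen after the landmark are handled. A time-dependent status has no new sample between week 12 and end of treatment, so late onset will be dated only roughly.
- If any-time tables of ORR or DOR are also shown, add a note that they cannot be read as an effect of ADA.

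The samples are already scheduled, so the cost is SAP wording and some programming. The ORR comparison will describe only patients who reached the landmark on treatment. Few of them will be ADA-positive, with fewer than one expected at C3D1 at 0.5% to 1% per month, so the result should be presented as descriptive, with individual patients listed.
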